We will utilize a modified MIT schedule for this PMIT study with a randomized, double-blinded study based on our previous experience with peanut-allergic subjects. Active peanut allergy will be confirmed in all interventional subjects with open oral food challenge prior to entry into the study. Control subjects may be offered a confirmatory food challenge if the diagnosis is uncertain. We will enroll 80 children in the intervention group. The active subjects will be randomized into either a high dose group (final maintenance dose of peanut 3000mg, N=40) or a low dose group (final maintenance dose of peanut 300mg, N=40) (see Figure 1). Forty additional subjects will be followed as control subjects and will not receive any type of study protein. All subjects in the active group will undergo a one-day peanut desensitization protocol designed to enable the subject to tolerate a daily dose of peanut protein (modified rush phase) (Table 3). If the subject has a mild reaction to one of the doses, the next dose would be determined at the discretion of the investigator. The options open to the investigator are to administer the last previously tolerated dose, or wait an additional amount of time between doses, or repeat the current dose. Once this determination of the dosage amount is made, the desensitization process resumes as outlined. Upon completion of the modified rush phase to peanut, the subject is observed for a minimum of 2 hours. If there is no evidence of an allergic reaction the subject is discharged home.

If the subject requires treatment for symptoms during the initial escalation protocol with antihistamines on one occasion, then the rest of the protocol may be followed. If the subject requires more than one medication or multiple doses of antihistamines or requires other rescue medications, the initial desensitization phase should be stopped. If the subject has tolerated either the 3 mg or 6mg dose, the subject will be eligible to return on Day 2 to proceed with the build-up phase.

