After the first day of desensitization, subjects will return to the research unit to begin the build-up phase of the study. The subject will ingest 6 mg, or a lower amount based on the reaction to the modified rush phase. After the subject is observed for a minimum of 30 minutes for symptoms to the study protein ingestion, he or she will be discharged from the research unit and will continue to consume the study protein at home daily for a minimum of ten to fourteen days (+7 days). The family receives the study protein doses as a powder that they give to the child each day by sprinkling it on a previously tolerated food (e.g., applesauce). Subsequently, subjects will return to the clinical research unit every ten to fourteen days to monitor their adherence to the dosage administration and increase the dose to the next escalation amount (see Table 4). The subject's response to the new dose escalation amount will be monitored for a minimum of 30 minutes after dose administration. Vital signs are performed prior to the dose administration, prior to the completion of the observation period before discharge, and anytime symptoms occur. If attempts at blood pressure measurement have been very disturbing and traumatic to a young child, the study team will rely on observation, heart rate and respiratory rate and the physical assessment to determine the subject's response. If the study team feels that a longer observation time is warranted based on the prior dosing history of the subject or their current physical status, the subject will be observed for a longer period of time. If symptoms occur that do not require treatment, the subject will be observed until they resolve. If symptoms occur that require diphenhydramine or albuterol, the subject will be observed a minimum of 2 hours or until symptoms resolve. If symptoms occur that require epinephrine, the subject will be observed at least 4 hours or until symptoms resolve. If symptoms do not fully resolve after 6 hours or if new symptoms occur, the subject will be transferred to UNC Children's Hospital to be observed overnight. Subjects will then take that dose daily for a period of 10 to 14 days (+ 7 days) after which they will return to the clinical research unit to have the daily dose increased proportionately at each visit until the maximum daily dose of study protein (3000mg) is consumed. All active subjects will build up to 3000mg of study protein. To maintain blinding, the subjects randomized to the 300mg peanut dose will have additional placebo flour added to the study protein during buildup by unblinded study personnel. Laboratory studies will be done at the beginning of the study, when the subject reaches the 156 milligram dose, when the subject reaches the 749 milligram dose, and when the subject reaches the 3000mg dose, and annually thereafter until the end of the study. The laboratory studies will consist of blood tests to monitor the immune response to the peanut protein. Stool studies will be performed at the beginning of the study and the end of the study. Control subjects will have visits for medical history, physical exam, titrated skin prick testing and blood and stool laboratory studies associated with the study at entry and then yearly. This control group will be seen yearly over the length of the study.

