Subjects who miss one to two days of the daily dose will continue at their current dose at home. The PI will determine where the next dose of study protein is given for those who miss three to four days of the daily dose based on the length of time on study, the daily dose amount, the subject's reaction history and the amount of time since the last reaction to a dose in order to assure safety with dosing. Those who miss more than four days will return to the clinical research unit for evaluation by the study team in order to determine the best course of action for the subject. Options open to the investigator include repeat desensitization, observed dosing at a dosing level previously tolerated by the subject, or a change from active subject to control subject. To monitor subjects for adherence, any accidental ingestion, any symptoms related to daily dosing and any unintended side-effects of daily dosing, the families will be asked to keep a simple daily diary to record the requested information. A copy of the daily diary is included on page 16 of the protocol.

We will monitor accidental reactions to peanuts in each subject during the PMIT trial. We will note any reaction that occurs in a subject after the ingestion of peanuts, and record the type of symptoms (i.e., skin, respiratory, gastrointestinal, or cardiovascular). Pilot data from our previous studies indicate that home dosing is safe, with infrequent reactions which are typically mild. These data have identified several risk factors for reactions, which include dosing on an empty stomach, fever/illness, and activity/exercise shortly after dosing. Families of subjects will be asked to administer the study protein with additional food such as at snack or meal times, and during illness to hold the study protein and contact study personnel for instruction.

Because of the extreme risk to subjects, those experiencing severe symptoms during dosing or challenges such as respiratory failure, hypotension or other symptoms requiring ICU care will be withdrawn from the study. Additionally any subjects who have had an accidental peanut ingestion and developed anaphylaxis with respiratory failure or hypotension during the time on PMIT will be dropped from the active portion of the study. Subjects that do not complete the study because of an accidental reaction to peanut will be followed in the control group.

Study Stopping Rules

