The following stopping rules will be used throughout the study. If a subject at any time point experiences a serious adverse event as described by the FDA or an unanticipated event of grade 3 or above as defined by the CTC III scale, the trial will be halted and the IRB and FDA will be consulted. If symptoms as noted above occur in 2 or more subjects, the study will be stopped and the situation reviewed. In addition, the study will not resume until the FDA has been notified and given the approval for the study to continue.

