Subjects will be dropped from the arm of the study ingesting daily maintenance dose of peanut protein if they are having moderate to severe clinical symptoms (GI, respiratory or skin) at home after taking the daily dose of peanut protein. Additionally, any subjects who have an accidental peanut ingestion and have anaphylaxis during the time on oral desensitization, will be dropped from the arm of the study ingesting daily maintenance dose of peanut protein. Subjects who experience peanut-related hypotension as evidenced by a 15 % drop in their blood pressure from their baseline, nontransient oxygen desaturation below 90%, recurrent abdominal pain, or recurrent emesis which is felt by the PI to be potentially dose related will be stopped from participating in the study.

Any subject who has a serious adverse event which is felt by the PI to be potentially a result of participation in the study will be dropped from the study.

SAFETY MONITORING

This section defines the types of adverse events that should be reported. It outlines the procedures for the appropriate collection, grading, recording and reporting of the events.

Procedures and Monitoring

All unexpected serious adverse events related to the experimental procedures will be reported to the IRB, DCRU, DSMB, and FDA in a manner consistent with 21 CFR 312.32. All other adverse events related to the experimental procedures will also be reported to the IRB and DCRU in an expedited manner if they are Grade 3 and above in severity. Participant deaths are reportable within 24 hours. The expedited report sent to other organizations will be copied to the DCRU. The investigator will continue to follow or obtain documentation of the resolution course of such an event. A copy of the annual report of adverse events submitted to the IRB will be copied to the DCRU. Reactions to dosing of the study product will be recorded on a dosing log and will not be reported separately as adverse events. Any reaction that meets the criteria for a serious adverse event will be reported both on the dosing log and on an adverse event case report form.

Definitions

Adverse Event (AE) or Medical Event

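### The Protocol lets treated children become controls, and the SAP does not say that they stay in the OIT group for analysis

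*Protocol*

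**What the plan says.** Protocol, Study Design, Dosage Schedule, and Accidental Reactions, gives two routes from active to control.

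- **Missed doses.** After more than four missed days the child is re-evaluated, and the options open to the investigator include "a change from active subject to control subject".
- **Accidental reactions.** "Subjects that do not complete the study because of an accidental reaction to peanut will be followed in the control group".

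The same section describes the control group differently: "Forty additional subjects will be followed as control subjects and will not receive any type of study protein". SAP, Sample size, likewise calls controls untreated and gives them an expected 20% spontaneous tolerance rate. The scheduled control procedures are limited: "Control subjects will have visits for medical history, physical exam, titrated skin prick testing and blood and stool laboratory studies", at entry and yearly. The only challenge mentioned for them is conditional: "Control subjects may be offered a confirmatory food challenge if the diagnosis is uncertain".

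SAP, Randomization, pools the two doses into one intervention group for the primary outcome. SAP, Statistical Analysis, compares E-OIT with controls by Fisher's exact test for baseline demographics and categorical peanut consumption outcomes. It fits generalized estimating equation models over time, one group at a time, for IgE, IgG4 and skin-test size. It names no analysis set and gives no rule for a child who changes status.

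**The concern.** A child who switches has already taken study protein, so cannot fit the description of an untreated control. The first route is worded as a change of status, not only of visit schedule. Two analysts could therefore place the same child in different groups and both claim to have followed the documents.

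The switch follows missed doses or a reaction, which are post-enrolment events plausibly related to outcome, and the first route is partly at the investigator's discretion. If children are analysed where they are followed, two things happen.

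- **Longitudinal curves.** Yearly blood and skin tests continue under the control schedule, so OIT-exposed data would enter the control curves.
- **SU rate.** The child leaves the OIT denominator and has no scheduled SU challenge. Those who miss doses or react are less likely to be successes, so the remaining rate probably flatters OIT.

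**Working it through.** **1. The plan's own figure.** SAP inputs: SU 70% v 20%, two-sided 0.05, 80% power. With mean proportion 0.45,

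n = [1.96·√(2·0.45·0.55) + 0.842·√(0.7·0.3 + 0.2·0.8)]² / 0.5² = (1.379 + 0.512)² / 0.25 = 14.3, so 15 per arm (power 82.0%).

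This reproduces. Allowing for 20% dropout, 15/0.80 = 18.75, so 19, and the SAP's 20 per arm covers it. No switch rate is given. If every dropout in the SAP's upper range were a switch, that would be 20% of 40 = 8 children. I use 0 to 8 as an assumed range, with 8 as the extreme.

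**2. Share of the control group** (40 controls, k switched): k/(40 + k).

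| k | Share |
|---|---|
| 2 | 2/42 = 4.8% |
| 4 | 4/44 = 9.1% |
| 8 | 8/48 = 16.7% |

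**3. Direction in the curves.** Let L be the switched children's change as a fraction of the mean change of all OIT starters. Assume no mean change in true controls and a simple difference at one time point; the SAP specifies no such contrast. With 40 OIT starters, the apparent difference relative to the true one is (40 − kL)/(40 − k) − kL/(40 + k). For k = 8 this is 1 − 8/48 = 0.83 if L = 1, and 40/32 = 1.25 if L = 0. The direction depends on L, which is unknown.

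**4. SU rate.** Suppose 20 of 40 starters reach SU (50%) and only non-SU children leave.

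| k | Apparent SU |
|---|---|
| 0 | 20/40 = 50% |
| 2 | 20/38 = 53% |
| 4 | 20/36 = 56% |
| 8 | 20/32 = 63% |

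**5. Type I error for SU.** Exact enumeration, true SU 20% among 40 OIT starters and among 40 controls, moved children all non-SU. The one-sample column is an exact test against 20% (upper tail, nominal 2.5%), which is my assumption because the SAP does not name that test. The Fisher columns are two-sided (nominal 5%) and require SU to be measured in controls.

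| k | One-sample | Fisher, switched join controls | Fisher, switched leave OIT only |
|---|---|---|---|
| 0 | 1.9% | 2.8% | 2.8% |
| 2 | 1.9% | 3.8% | 4.0% |
| 4 | 4.3% | 5.7% | 3.9% |
| 6 | 4.3% | 8.4% | 5.3% |
| 8 | 8.8% | 12.4% | 6.1% |

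If the moved children's own SU rate is 10%, the joined-to-controls Fisher error is 4.2% (k = 4) and 5.8% (k = 8). If it is 20%, it stays below 4%. For a single arm of 20 the one-sample figure goes from 1.0% to 3.2% with 1 to 4 moved. With the Protocol's 80 active children it is 2.2% (0 or 2), 3.9% (4 or 6) and 6.6% (8).

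**The case against.** The strongest reply is that the documents already point to an answer. Controls are defined as children who receive no study protein, so an OIT-exposed child is not one, and being followed in the control group can mean visits alone. That is a fair reading of the accidental-reaction sentence. It is weaker for the missed-dose sentence, which changes the child from one kind of subject to the other, and nothing in the SAP settles it.

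The reply also cuts down the size of the problem, and most of that stands:

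- The loss from the SU denominator is what any dropout does and is not peculiar to switching. The one-sample column above belongs to that general problem.
- The part specific to switching is the gap between the last two columns. There is no added error at 2 moved, and the larger gaps need every moved child to be non-SU.
- No SU challenge is scheduled for controls, and it is unclear whether the Fisher comparison covers SU at all.
- The SAP names no between-group contrast for the longitudinal models, so step 3 shows only that the direction is open.

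A reader might infer that the plan analyses switched children as controls and so runs a false-positive risk of about 12%. The documents do not support that. No sentence assigns them to the control analysis, and the 12.4% needs eight switches, all non-SU, plus SU results in controls.

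Nor is there a general transfer of failures. Children who fail a challenge resume dosing or complete the study, and those with severe symptoms during dosing or challenges are withdrawn. The study-level rule ("If symptoms as noted above occur in 2 or more subjects, the study will be stopped and the situation reviewed") may further limit switches after severe accidental reactions, though not missed-dose switches.

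**Conclusion.** The point holds as a stated rule with no matching analysis rule. Read literally, the Protocol puts OIT-exposed children into a group that both documents define as untreated, and the SAP does not undo it. It should be fixed.

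The surest consequence is for the control IgE, IgG4 and skin-test curves, because those data are scheduled for controls. The direction is unknown, and the share is 4.8% to 16.7% for an assumed 2 to 8 switches. For the SU rate the bias probably favours OIT, as ordinary dropout would. In the pooled 40, type I error passes its nominal level only with about four or more switches, nearly all non-SU, and passes it through the control group only if SU is measured there. All sizes are conditional, since no switch rate is given.

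The planned 70% v 20% conclusion is not in danger. With 8 of 40 switched and kept as failures, 22/40 against 8/40 still gives Fisher p = 0.002. What is at stake is the reported effect size and the meaning of the control curves.

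**What to change.** **SAP.** State that:

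- every child who started OIT is analysed in the OIT group, and by randomised dose for the dose comparison, whatever visit schedule is followed later;
- switched children are excluded from all control summaries, tests and longitudinal models;
- a switched child without a passed SU challenge counts as not SU in the primary SU rate, with a completers analysis as sensitivity;
- switches are reported by arm and reason.

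**Protocol.** State that control status after a switch refers to the visit schedule only.

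**Cost.** A few sentences and no new visits. The SU rate becomes slightly less favourable. Power, assuming 70% SU in 16 evaluable children per arm (20 less 20%) and 20% in 40 controls:

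| Switched children added back as not SU | Power |
|---|---|
| One arm, exact test against 20%: 0, 1 or 2 | 97% throughout |
| One arm v 40 controls, Fisher: 0, 1 or 2 | 94%, 91%, 87% |
| Pooled OIT v 40 controls, Fisher: 0, 4 or 8 | 99%, 97%, 91% |

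In the extreme where all four dropouts in an arm are switches, the one-arm figures are 93% (exact) and 80% (Fisher).

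Controls are not randomised, so this removes an avoidable selection but does not make OIT v control a randomised comparison.

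**Separate point.** The design section removes a child from active treatment when an accidental ingestion "developed anaphylaxis with respiratory failure or hypotension during the time on PMIT will be dropped from the active portion of the study", while Individual Stopping Rules stops maintenance dosing for "any subjects who have an accidental peanut ingestion and have anaphylaxis during the time on oral desensitization". The two passages must be reconciled; the analysis rule above does not depend on how.

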The present research plan draws upon our extensive knowledge of the allergens involved in peanut hypersensitivity; it is also based upon evidence demonstrating the effectiveness of peanut oral immunotherapy (OIT) in preliminary research studies. Previous attempts to utilize peanut-specific immunotherapy (IT) subcutaneously have failed primarily because of the side effects of therapy. We expect PMIT to have fewer side effects than the non-mucosal systemic desensitization method, and this proposal will compare a high dose regimen to a low dose regimen, which may improve the safety profile of PMIT. We propose to test the efficacy of PMIT in young peanut-allergic subjects; we believe that early intervention with PMIT, prior to the development of sustained immunologic memory, may offer an optimal treatment for affected subjects.

Our **hypothesis** is that mucosal peanut immunotherapy will make subjects who have peanut allergy less allergic and induce changes in their cellular and humoral immune system.

The proposed study has two primary **objectives**:

Objective #1: To treat peanut-allergic subjects with PMIT and to determine whether this protocol lowers their risk of anaphylactic reactions and causes long-term tolerance.

Objective #2: To determine the effect that PMIT has on the peanut-specific cellular and humoral response in peanut-allergic subjects.

Objective #1: To determine whether PMIT reduces peanut induced anaphylactic reactions and induces long-term tolerance in peanut-allergic subjects.

Purpose and expectations:

These studies are designed to test the feasibility and effectiveness of using PMIT to desensitize subjects with peanut allergy, and to optimize the appropriate treatment dose. We expect to demonstrate the effectiveness of PMIT by showing that subjects on PMIT will have negative double-blind placebo-controlled food challenges (DBPCFC) to peanuts following completion of a 36-month course of PMIT. We will compare the effects of high-dose PMIT (3000mg) and low-dose PMIT (300mg) against untreated controls, and we expect that PMIT will induce a significant decrease in: (a) wheal (swelling) size from a titrated skin prick test to peanut protein, (b) serum-specific IgE to peanut, and (c) adverse effects with accidental peanut ingestion. In this study we will test the hypothesis that low-dose PMIT is as successful in tolerance induction as high-dose PMIT in a young cohort of newly diagnosed subjects.

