The significance of this proposal is several-fold. First, a treatment for peanut-allergic children is badly needed. A therapeutic option such as PMIT would greatly benefit subjects both immediately, by preventing anaphylactic or significant allergic reactions to small amounts of peanuts in other foods, and long-term, by laying the groundwork for development of an optimal vaccine for peanut allergy. Second, an understanding of the cellular and humoral dynamics following PMIT will allow us to determine if this is an appropriate initial step in the eventual development of a safe and efficacious vaccine/treatment for peanut-allergic subjects. This proposed study would also generate important new pharmacodynamic information about PMIT by targeting newly diagnosed young patients. We believe that the initiation of treatment soon after diagnosis and early in life, as well as the comparison of doses, will generate novel data that are likely to impact the safety and efficacy of future PMIT therapies. Additionally, targeting young populations with PMIT may also generate useful insights about tolerance that could be applied to implementation of primary prevention strategies before peanut allergy develops. If PMIT does not induce complete tolerance, it may be partially effective and useful in augmenting other types of therapy including antihuman IgE or other peanut-specific vaccines. Finally, a better understanding of the immunologic process by which allergen desensitization occurs during PMIT can later be applied to other food allergies.

1. Urgent need for an effective treatment/prevention strategy

It is estimated that over 50% of individuals who are allergic to peanuts will have an accidental reaction to peanuts over a two-year period. Previous studies have examined traditional and rush allergen IT in peanut-allergic subjects. Given the partial rate of response and the high rate of adverse reactions in these studies, and considering the frequent occurrence of accidental peanut ingestion, alternative forms of immunotherapy are necessary for this potentially fatal allergy.

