12	100mg	2	25%
13	125mg	2	25%
14	156mg	2	25%
15	195mg	2	25%
16	245mg	2	25%
17	306mg	2	25%
18	383mg	2	25%
19	479mg	2	25%
20	599mg	2	25%
21	749mg	2	25%
22	936mg	2	25%
23	1170mg	2	25%
24	1463mg	2	25%
25	1829mg	2	25%
26	2286mg	2	25%
27	3000mg	2	31%

Tolerance of Daily Study Protein Dose Diary

Child's Name _____

Date							
Dose taken (Yes or No)							
Accidental ingestion (Yes or No)							

Using the following scale, please enter the appropriate number in each box
 0 = None 1 = Mild 2 = Moderate 3 = Excessive

Vomiting							
Diarrhea							
Hives							
Itching							
Runny Nose							
Wheezing							
Other							

Comments:

DEVIL Screening Form

Screening _____ Date _____
Recorded by _____

Informed consent obtained and witnessed prior to obtaining information: Yes No

Copy of informed consent given to parent: Yes No

Name _____ Unit # _____

Parent's Name _____

Address _____

Telephone number that we can personally reach you: (H) _____
(W) _____ (Cell) _____

DOB _____ Age _____ (between 9 and 36 months of age)

Sex: Male Female Race: Afr-American Caucasian Hispanic Other

Weight _____ (lb kg) Height _____ (in cm)

Ever eaten peanut? Yes No Not Sure

Describe reactions to peanut and other foods:

Eligibility Criteria

_____ Subject between 9 and 36 years of age

_____ Peanut allergy diagnosis within the last 6 months: CAP > 0.35 or PST > 3mm with history of peanut ingestion & convincing IgE-mediated symptoms within 60 minutes

date of reaction: _____

date of testing (and results): PST _____ (_____) CAP _____ (_____)

Or

_____ Probable peanut allergy diagnosis within the last 6 months: CAP > 5 and PST > 3mm with NO history of peanut ingestion

date of testing (and results): PST _____ (_____) CAP _____ (_____)

Exclusion

_____ Subjects with a history of severe, anaphylaxis to peanut

_____ Medical history that would prevent a DBPCFC/OFC to peanut

Desensitization Day

Initial Medical History & Physical Exam

Subject Name: _____ D.O.B: _____

Subject # _____ Race: _____

Atopic History: (Symptoms, triggers, current treatment, date of onset/diagnosis)

Rhinitis _____

Atopic Dermatitis _____

Food Allergy _____

Drug/Venom allergy _____

Asthma _____

Patient has a current in-date EpiPen

Yes: Date expires _____

No:

Patient was given an EpiPen

Yes: Date expires _____

No:

Episodic symptoms/brief and intermittent with complete clearing/ greater than twice a week/continuous?

_____ Coughing _____ Chest Tightness _____ Wheezing _____ SOB

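### Accidental peanut reactions are to be compared with untreated controls, but the plan records them more closely in treated children than in controls and does not define the outcome, so the comparison cannot be interpreted as written.

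*Protocol*

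**What the plan says.** In the Protocol, under Objective #1 (Purpose and expectations), the plan is to "compare the effects of high-dose PMIT (3000mg) and low-dose PMIT (300mg) against untreated controls". Among the outcomes expected to fall significantly is "c) adverse effects with accidental peanut ingestion".

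The section on study design, dosage schedule and accidental reactions describes how events are recorded:

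- **Treated children.** The diary's stated purpose is "To monitor subjects for adherence, any accidental ingestion, any symptoms related to daily dosing and any unintended side-effects of daily dosing", and to that end "the families will be asked to keep a simple daily diary to record the requested information". The form itself, printed after the dosing table, is headed "Tolerance of Daily Study Protein Dose Diary". It has a row for whether the dose was taken, a yes/no row for accidental ingestion, and symptom rows. During build-up these children return to the research unit every 10 to 14 days.
- **Controls.** They receive no study protein. They have a history, examination, skin test and laboratory studies at entry and once a year after that: "This control group will be seen yearly over the length of the study". No diary or interim scheduled contact is described for them.
- **All children.** The protocol says that accidental reactions will be monitored in each subject. It gives every family phone, pager and e-mail routes to study staff for questions or concerns.
- **Moves between groups.** Children who do not complete the study because of an accidental reaction are followed in the control group.

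The SAP (Statistical Analysis) names baseline demographics and categorical peanut consumption outcomes as comparisons with controls. It names no analysis of accidental reactions.

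**The concern.** An outcome compared between groups has to be looked for in the same way in each. Here one group has a daily prompt and, for part of the study, a visit about every two weeks. The other has an annual history and whatever families choose to report in between. Mild and moderate reactions are the ones most likely to be forgotten or left undated over a year, and the protocol intends to note any reaction, not only severe ones.

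At stake is a named expectation under one of the two primary objectives. A difference in recording could hide a real reduction in reactions, or produce an apparent difference where there is none. Events never recorded cannot be recovered in the analysis.

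**Working it through.** The documents give no rate, power or sample size for accidental reactions, so there is no stated figure to reproduce. The check has four steps.

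**1. Recording, side by side**

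| | Treated | Controls |
|---|---|---|
| Daily diary with accidental-ingestion row | Yes | None described |
| Scheduled visits, build-up | Every 10–14 days | Entry, then yearly |
| Scheduled visits, 36-month maintenance | No interval stated; annual laboratory studies | Yearly |
| Family may contact staff | Yes | Yes |

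The dosing table lists 20 steps after 6 mg (doses 8 to 27) at two-week intervals, so build-up takes about 20 × 2 = 40 weeks. After that, the documented difference rests on the diary.

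**2. Effect on a rate of reactions**

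Observed ratio = true ratio × (treated capture ÷ control capture). The capture fractions are assumptions: 1.0 for treated and 0.5 to 0.8 for controls.

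- True ratio 0.50: 0.50/0.8 = 0.63; 0.50/0.5 = 1.00.
- True ratio 1.00: 1/0.8 = 1.25; 1/0.5 = 2.00.

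If the diary captures only 90%, a true 0.50 appears as 0.50 × 0.9/0.8 = 0.56 up to 0.50 × 0.9/0.5 = 0.90. Equal capture in both groups removes the distortion.

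**3. Scale at the protocol's group sizes**

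The Protocol (Expected Impact, item 1) states that "over 50% of individuals who are allergic to peanuts will have an accidental reaction to peanuts over a two-year period". Take 0.50 as the control two-year risk, 80 treated and 40 controls, a true risk ratio of 0.50 (treated risk 0.25) and full capture in treated children. Power is for a two-sided 0.05 test, normal approximation, in the direction favouring treatment:

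| Control capture | Observed control risk | Observed risk ratio | Power |
|---|---|---|---|
| 1.00 | 0.50 | 0.50 | 78% |
| 0.90 | 0.45 | 0.56 | 60% |
| 0.75 | 0.375 | 0.67 | 30% |
| 0.50 | 0.25 | 1.00 | 2.5% |

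These powers apply only to the protocol's planned sizes. The SAP reports 20 enrolled per treatment arm and gives no control number.

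**4. Whether the direction is fixed**

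The outcome can also be read as the chance of reacting given an ingestion. Suppose that chance is 0.50 in both groups, treated families log every ingestion, and control families recall every reaction but only a share q of symptom-free ingestions. The observed control proportion is 0.50/(0.50 + 0.50q):

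- q = 0.50: 0.50/0.75 = 0.667, observed ratio 0.50/0.667 = 0.75
- q = 0.25: 0.50/0.625 = 0.80, observed ratio 0.63
- q = 0.10: 0.50/0.55 = 0.909, observed ratio 0.55

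With no true effect, treatment now looks better. The reassignment rule can push the same way: a treated child who stops after an accidental reaction enters control follow-up, and no document says in which group that child is analysed.

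**The case against.** The strongest defence is that the protocol does commit to monitoring accidental reactions in each subject, tells every family how to reach staff at any time, and nowhere says that controls lack a diary. That is correct, and it rules out the flat statement that reactions in controls are recorded only at yearly visits. But the commitment comes with no instrument or schedule for controls. Calling in is passive and equally open to treated families, so it does not even out the recording. The absence of a control diary is an inference from the form's title and rows and from its stated purposes, all but one of which concern dosing or adherence. It is a reasonable inference, not a stated fact.

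A reader might infer that the comparison is simply biased against treatment. The documents do not support that. It follows for a count or rate of reactions, but reverses for reactions per ingestion, and moving children into control follow-up can also favour treatment.

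A reader might also infer that the main efficacy result is compromised. It is not. The primary endpoint is assessed by food challenge, the SAP's sample size rests on sustained unresponsiveness, and accidental reactions have no planned test. Anaphylaxis, the event in Objective #1, is also the kind of reaction that families are least likely to forget.

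Two further points stand. The 50–80% range has no source in the documents, and full diary capture over years is optimistic. Nor would common recording make the comparison causal: only treated children are randomised (between doses), and controls are offered a confirmatory challenge only if their diagnosis is uncertain.

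**Conclusion.** The concern holds as one of unequal recording combined with an undefined outcome. The plan sets up a comparison with controls on accidental reactions but describes an active, prospective record whose content fits treated children only. Following the plan as written would give an outcome that is not comparable between groups.

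The size can only be illustrated. For a rate of reactions, with 50–80% capture assumed in controls and full capture in treated children, a halving of the rate would appear as a ratio between 0.63 and 1.00. The net direction stays undetermined until the denominator and the handling of moved children are fixed. This is a cheap improvement to a secondary expectation, not a threat to the trial's main result.

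**What to change.** 1. From enrolment, give control families the accidental-ingestion and symptom lines of the diary, or use one brief scheduled report that is the same in all groups. Returns can use the phone or e-mail routes that the protocol already provides.
2. Define the outcome in the SAP as accidental reactions per child-year, reported by severity.
3. Analyse every child in the original group, including those later moved to control follow-up.
4. Label the comparison with controls exploratory, since controls are not randomised.
5. If common recording is not adopted, remove expectation (c) as a comparison with controls and report accidental reactions within the treated groups only.

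The cost is a short form, a protocol sentence and a few lines in the SAP, with no extra visit or procedure. The downside is a modest reporting burden for control families, which should not be dismissed because participation can last up to 72 months; a brief periodic report would be lighter than a daily diary, provided that the same report is used in every group. The fallback in item 5 adds no data collection.
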